- for social workers and family support workers: the social worker or family support worker was a member of a team assigned to the intervention at point of randomisation and 0 else;
- for foster / kinship carers: the carer cares for a child or young person whose case is held at the point the foster carer enters the sample, by a social worker who is a member of a team assigned to the intervention at point of randomisation and 0 otherwise.

Although there is some turnover of social workers, family support workers and foster carers, about 80% of those at T0 (April 2021) will still be working with the local authority at T13 (May 2022), and so 80% will have received the full 12 months of the intervention. Binarising the treatment seems a reasonable proxy in this case.

For the outcomes relating to children, treatment is coded as a binary variable. When children enter the sample, at either the point of randomisation, or the point they become eligible (e.g. their case opens and meets other criteria) they will be allocated to treatment if the team of their allocated social worker was randomised to treatment.

Covariates

Including control variables increases the precision of the estimate. In each regression, we control for a number of relevant covariates. We outline different categories of covariates below.

Site effects

We include site fixed effects but not site-treatment interaction terms.

Previous outcome measures

We control for the previous measurements of the outcome variable where data is available. For the survey-based measures for social workers, family support workers and foster carers, the same measures will be asked at T6 (October 2021) and T13 (May 2022), and for administrative data we expect previous values to be available. For the outcomes of the CYP and parents / carers (including kinship carers), the previous measure of the outcome will be at T0 (April 2021) or when they entered services if they entered services after T0 (April 2021).

Other covariates

For CYP outcomes (primary outcome i) and secondary outcome i)), we include the following vector of individual-level covariates:

- gender (coded as male, female, or other/missing)
- age group (4-11, 12-17, 18 years, or missing with 4-11 as the reference category)
- ethnicity (Asian / Asian British, Black / African / Caribbean / Black British, Mixed / Multiple ethnic groups, Other ethnic group, White, missing; with the majority group as the reference category)

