- disability status (Yes, No, Don't know/missing with No as the reference category)
- most recent type of CSC intervention (coded as :
 - Child in Need
 - Child Protection Plan
 - Looked After - LA fostering / kinship care
 - Looked After - IFA / other LA fostering other placement type
 - missing;
 - with Child in Need as the reference category)

- unaccompanied asylum seeking child (yes, no, or missing with no as the reference category)
- if possible, whether their social worker has changed over the intervention period (yes, no, missing with no as the reference category)
- for the primary outcome 1-3 only, the number of status changes within the intervention period (numeric: as per the children's social care interaction outcome variable)

For social worker and family support worker outcomes, we include the following individual-level covariates:

- gender (coded as male, female, or other/missing),
- role (social worker, family support worker, or missing; with social worker as the reference category)
- contract type (permanent, agency or missing; with permanent as the reference category)
- the number of years experience (Associated and Supported Year in Employment / years<1, 1≤ years<4, 4≤years<9, 9years<15, ≥15 with ASYE as the reference category)

We include the following team-level characteristics (measured at T0):

- team type as categorised in Table 1 above (CINP / CPP, CLA, children with disabilities with CINP / CPP as the reference category)
- team size (numeric)
- percentage social worker or family support worker (numeric)
- percentage permanent or agency workers (numeric)

For foster carers (where we can match the data):

- gender (coded as male, female or other/missing)
- employer (LA foster carer, employed by an independent fostering agency or another local authority, or missing; with LA foster carer as the reference category)
- number of years experience (numeric)

Where the foster carer answering the survey is different between pre and post intervention data collection (e.g. the foster carer who answered at baseline isn't available or no longer fosters the child), the post data will be collected from the available foster carer and their pre data will be recorded as missing. The data collected from the foster carer who answered at the pre data collection point will be discarded (we won't impute their outcome data).

Please see the regression specification.

Standard errors

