- For each outcome, we will regress an indicator of missingness on the covariates in the main model (see the “Covariates” section) using logistic regression with standard errors clustered at the team level. If any of the coefficients on the covariates of the missingness model are statistically significant at the 5% level, then data is not missing completely at random (MCAR).
- In particular, we are interested in the coefficient on the treatment dummy. If it is not significant, this suggests that the data is missing experimentally at random (MEAR) (where data may be correlated with observable or unobservable variables, but not with treatment assignment) and we will only include observations for which we have the outcome data controlling for any variables which are significant (if they are not already specified in the “Covariates” section above).
- In line with WWCS statistical guidance, if the data on outcomes is missing experimentally not at random (MENAR) e.g. due to large differential attrition, then we will multiply impute within the treatment condition.

Sensitivity analysis following multiple imputation

Given that there may be a substantial proportion of outcome data to impute, we check the sensitivity of our results to the imputation strategy. We will:

²¹ See Taljaard, M., Donner, A., & Klar, N. (2008). Imputation strategies for missing continuous outcomes in cluster randomized trials. *Biometrical journal. Biometrische Zeitschrift*, 50(3), 329–345. <https://doi.org/10.1002/bimj.200710423>

- impute using baseline observation carried forwards (BOCF)
- impute using control drifted observation carried forward (CDOCF). This is done by carrying forward the baseline observation and then adding the “drift” from the comparator group to take into account the amount their outcome would have changed in the absence of treatment. The drift is calculated using an autoregression model for the comparator group.

Reporting

In addition to handling missing data and conducting sensitivity analyses, we also report some summary statistics to allow for a qualitative assessment of the impact of missing data on the treatment effect estimate.

- For each outcome and covariate, we will report the percentage of missing data alongside summary statistics
- Rates of loss to “post” data collection for the arms of the trial

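### Foster carers replaced by another respondent at follow-up are discarded and barred from imputation, an exception that the missing-outcome plan does not recognise

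*Protocol*

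**What the plan says.** Two parts of the Protocol's analysis plan apply to a carer who answers the first survey but not the last.

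- **Covariates, Other covariates (foster carers).** The rule applies when the follow-up respondent is a different carer, for example because the first is unavailable or has stopped fostering that child. In that case "the post data will be collected from the available foster carer and their pre data will be recorded as missing". Of the first carer it says "The data collected from the foster carer who answered at the pre data collection point will be discarded", adding in brackets "we won't impute their outcome data".
- **Missing data strategy, Outcomes.** "For each outcome, we will regress an indicator of missingness on the covariates in the main model". The coefficient on treatment is singled out. If it is not significant, only observations with an outcome are analysed. If outcomes are missing differentially by arm (the protocol's MENAR case), "then we will multiply impute within the treatment condition". Two sensitivity analyses follow imputation, baseline observation carried forward (BOCF) and its control-drifted variant (CDOCF). Both start from the missing person's own earlier value.

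The treatment definition codes a carer by the team holding the child's case when the carer enters the sample. It also expects that "about 80% of those at T0 (April 2021) will still be working with the local authority at T13", a figure pooled over social workers, family support workers and carers.

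**The concern.** A carer with a first-survey score and no final score is the case the missing-outcome plan is written for. The carer rule removes that case before the plan is applied and puts another person's answer in its place.

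Losing a placement or giving up fostering happens after allocation, and Kitbag could plausibly influence it. If it happens at different rates in the two arms, the comparison becomes one of stayers plus replacements, and the diagnostic meant to reveal differential loss does not include the carers who were replaced.

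The rule also fits the rest of the design poorly. The regression is written for an individual carer, and the Data collection schedule surveys in-house foster carers without sampling. A carer who still fosters for the authority but no longer looks after one particular child is nevertheless discarded, although a T13 answer may be obtainable.

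**Working it through.** No stated figure can be reproduced: the carer outcome has no power calculation, and the protocol's one MDES concerns children. The check is a comparison of the rules, then an estimate of scale.

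**1. A replaced carer traced through the missing-outcome plan**

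| Step | Plan as written for each outcome | After the discard rule |
|---|---|---|
| Missingness indicator | carer counts as missing | no record, so not counted |
| Test against treatment | carer contributes | carer does not contribute |
| Missingness unrelated to treatment | complete cases; carer drops out | same result for the discarded carer |
| Missingness related to treatment | imputed within arm | imputation barred |
| BOCF and CDOCF | first score carried forward | first score no longer held |

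The direct conflict is therefore in the differential-missingness branch. The test that selects the branch is affected as well.

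**2. How many carers**

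Inputs: 424 carers in the intervention group (Table 2); about 20% gone by T13 (100% minus the stated 80%); 10% survey response (Data collection schedule).

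- Carers leaving: 424 × 0.20 = 84.8
- First-survey respondents: 424 × 0.10 = 42.4
- First-survey respondents leaving: 42.4 × 0.20 = 8.5

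The 20% runs from T0, but the carers' first survey is at T6. Assuming a constant leaving rate, 8.5 × 7/13 = 4.6. Only leavers whose replacement answers trigger the rule, which lowers the count. Placement changes among carers who stay with the authority raise it. The number of control-arm carers is not given.

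**3. How large the distortion could be (assumed inputs)**

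Suppose 15% of intervention and 25% of control carers are lost, and leavers score d lower than stayers. Dropping them hides (0.25 − 0.15) × d:

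- d = 0.5 SD: 0.05 SD
- d = 1.0 SD: 0.10 SD

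This formula leaves out replacements' answers. A simulation includes them: no true effect, pre-post correlation 0.73 (the scale's stated test-retest value), lower scorers more likely to leave, replacements drawn from the general carer distribution, unadjusted means. Differences, intervention minus control, in SD:

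| Turnover, control / intervention | Stayers plus replacements | Stayers only | All first-survey carers | BOCF for leavers |
|---|---|---|---|---|
| 20% / 20% | 0.005 | 0.005 | 0.004 | 0.004 |
| 20% / 15% | −0.027 | −0.043 | −0.003 | 0.005 |
| 20% / 10% | −0.051 | −0.077 | 0.001 | 0.022 |
| 25% / 15% | −0.048 | −0.083 | −0.005 | 0.013 |

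With equal turnover the rule does no harm. With a 10-point difference it produces about −0.05 SD where the truth is zero.

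**4. What the missingness test could detect with every carer kept**

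Assume 42 respondents per arm (the control number is an assumption), loss of 10% versus 20%, and no clustering. SE = √[(0.10 × 0.90 + 0.20 × 0.80)/42] = √(0.25/42) = 0.077. Then 0.10/0.077 = 1.30, and two-sided power at 5% is about Φ(1.30 − 1.96) = Φ(−0.66), or roughly 25%. Keeping the carers makes the test valid but not powerful.

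**The case against.** The strongest defence is that the carer rule is a deliberate, specific exception. Its bracket shows the authors had imputation in mind, and it can be read as measuring the child's current carer. On that reading the outcome is observed and the missing-outcome plan is not triggered. Carers were not themselves randomised and enter over time, so following the current carer could be a legitimate choice of target. This would carry weight if the plan said so. It does not: the missing-outcome section admits no exception, the model is for an individual carer, and a carer's arm is fixed at that carer's own entry.

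Other parts of the defence stand.

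- A reader might infer that the sensitivity analyses lose their baseline values altogether. They do not: only replaced carers' values go.
- A reader might infer that the two sections conflict throughout. When missingness is unrelated to treatment, both exclude the first carer.
- A reader might infer that replacement leaves no trace or vanishes from the reports. The replacement's earlier score is recorded as missing and so enters the covariate missingness check, though mixed with new entrants and first-survey non-response. The protocol also promises loss rates by arm and a baseline table by response. It does not say whether discarded carers are counted there.
- Imputation from a T6 score cannot recover a fall that came after T6, and someone who has stopped fostering may have no meaningful T13 score.

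**Conclusion.** The point holds in a limited form. The discard rule takes replaced carers out of the missingness test and, if outcomes are differentially missing, out of imputation and both carried-forward analyses, without the missing-outcome plan acknowledging it. Secondary outcome 5 is then open to bias if replacement differs by arm.

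A reader might take 0.05-0.10 SD as the bias built into the plan. The documents do not support that: the 10-point differential and the 0.5-1.0 SD gap are both assumptions, and equal turnover gives essentially none. About 8 intervention-arm respondents, possibly fewer, are affected on one of five secondary outcomes. The primary outcome is untouched. It is worth correcting because the change is small, not because the effect is known to be large.

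**What to change.** Delete the sentence that discards the first carer's data and bars imputation. In its place:

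1. Keep every first-survey carer in the arm fixed when they entered the sample.
2. Seek that carer's T13 response even if they no longer look after the same child.
3. If there is no response, count the outcome as missing under the existing missing-outcome plan and include the carer in the loss-by-arm reporting and the baseline table by response.
4. Treat a replacement carer as a separate new entrant, coded by the existing entry rule.

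This is a wording change that relies on first-survey data the plan already intends to collect. The cost is a little more follow-up and analysis work. The report should state that imputation from the T6 score does not capture change after T6.
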